9.2.2.3. Serology for HIV, Hepatitis B, Hepatitis C, and Cytomegalovirus

In the Phase 1 portion of this study, a blood sample will be drawn at the Screening Visit or before the first infusion for assessment of hepatitis B, as well as antibodies to cytomegalovirus antigen. Blood samples will be drawn for assessment of antibodies to cytomegalovirus antigen after study drug administration.

In the Phase 2 portion of this study, a blood sample will be drawn only at the Screening Visit for the assessment of hepatitis B, hepatitis C, HIV, and antibodies to cytomegalovirus antigen.

9.2.2.4. Pregnancy Test

As of Amendment 8, serum pregnancy tests will continue to be performed by the local laboratory on samples collected every 4 weeks during the Treatment Period (see Table 3).

A blood sample will be drawn at the Screening Visit or before the first infusion from all women of childbearing potential. The sample will be shipped to the central laboratory (BARC) for immediate analysis of human chorionic gonadotropin. Pregnant women will not be allowed to take part in this study and will be considered as screening failures.

Women are considered of childbearing potential unless they have undergone hysterectomy or tubal ligation within 1 year or have been postmenopausal for at least 1 year before the Screening Visit or before the first infusion

9.2.3. Myeloma-related Laboratory Efficacy Assessments

As of Amendment 8, efficacy laboratory assessments will be performed by the local laboratory and disease/response evaluations will be based on local institutional practice (see Table 4 and Attachment 9). Response to therapy will be evaluated by using the International Myeloma Working Group Uniform Response Criteria. Skeletal surveys will only be done if a subject has developed new symptoms.

9.2.3.1. Bone Marrow Assessments

Bone marrow biopsy and/ or aspirate will be performed at visits as indicated in Table 1 and Table 2. The samples will be evaluated histologically for assessment of the percentage and monoclonality of plasma cells, and determination of other cells in the marrow. An aspirate will be evaluated by flow cytometry with CD45, CD38, CD56, CD138, CD19, CD28, CD117, cytoplasmic light chain kappa/lambda, cytoplasmic IgA+ and IgG+, CD20, and CD27 to characterize CD38, CD46, CD55, and CD59 expression in myeloma cells, as well as to characterize T, B, and NK cells. If the subject's platelet count is low, a platelet transfusion may be given before the bone marrow sampling at the investigator's discretion.

9.2.3.2. Serum Immunoglobulin A, M, and G (M-component)

A blood sample will be drawn for quantitation of M-component by serum protein electrophoresis at visits as indicated in Table 1 and Table 2. Subsequent Ig identification will be done by immunofixation. If the M-component is IgD or IgE, these Ig types should be included in the analysis. A second aliquot of serum shall be stored and analyzed as needed, if daratumumab interference is suspected in the post-treatment serum immunofixation assay.

9.2.3.3. Urinalysis for M-component

A 24-hour urine sample will be collected at the Screening Visit or before the first infusion, on the first day of each cycle, at the EOT, and at all follow-up visits for quantitation of total protein (including albumin) and CrCl, for quantitation of M-component by electrophoresis, and for immunofixation.

Additional sampling may be performed at the investigator's discretion.

9.2.3.4. Serum Free Light Chain Ratio

A blood sample will be drawn for quantitation of the free light chain ratio by immunonephelometry at visits as indicated in Table 1 and Table 2.

9.2.3.5. Prognostic Factors- Phase 1 only

A blood sample will be drawn at the Screening Visit or before the first infusion for later analysis of prognostic factors. The blood sample will be stored at the central laboratory (BARC) for up to 1 year after the last subject's last visit. Analysis of prognostic factors may be done in batches of several samples. Subjects will be asked to sign a separate informed consent form for this analysis.

Prognostic factors indicative of altered responsiveness to treatment and/or survival that may be analyzed include the following:

- Serum β_2 -microglobulin and serum albumin in accordance with the International Staging System for multiple myeloma (Greipp 2005) 7
- Genetic anomalies such as 17p deletion; translocations including t(4,14), t(6,14), t(11,14), t(14,16), t(14,20), t(20,20); and hyperdiploidy

9.2.4. Pharmacokinetics and Immunogenicity Assessments

As of Amendment 8, blood sample collection will stop and not be performed after the last dose of daratumumab. One final sample should be taken before the start of the last infusion per Amendment 7.

Phase 2: Samples to assess both the serum concentration (pharmacokinetics) of daratumumab and the generation of antibodies to daratumumab (immunogenicity) will be obtained from all subjects according to the Time and Events Schedule (Table 2). At specified time points, venous blood samples (5 mL per sample) will be collected and the serum will be divided into 3 aliquots (1 aliquot for pharmacokinetic analysis, 1 aliquot for immunogenicity assessment [when appropriate], and 1 aliquot as a back- up). Blood samples should not be drawn from the arm in which the infusion was administered.

The exact dates and times of blood sampling must be recorded. Refer to the Laboratory Manual or equivalent document for sample collection requirements. Collected samples must be stored under the specified and controlled conditions for the temperatures indicated in the laboratory manual.

Table 10: Phase 1 Sample Collection Times for Determination of Daratumumab Concentration in Serum

									Study	Visits						
Sample Collection		Screening			Cycle	1			Cyc	le 2 ^a		Cycl	e 3-6	Cycle 7-24	FU	EOT
	Visit Number	0	1	2	3	4	5	1	2	3	4	1	2	1	1-6	_
	Day/Week/Month	≤21 days before Visit C1-1	0d	1d	1w	2w	3w	1d	1w	2w	3w	1d	2w	1d	Monthly	
	Visit Window	_	_	_	±1d	±1d	±1d	±4d	±1d	±1d	±1d	±4d	±1d	±4d	±7d	±2d
Before infusion			X	X	X	X	X	X	X	X	X	X	X	X^{b}	X^{b}	X^{b}
End of infusion			X	X	X	X	X	X	X	X	X	X	X	X		
+ 2 hours after infusion				X							X					
+ 5 hours after infusion				X												
+ 12 hours after infusion				X												

d = day; EOT = End of Trial; FU = Follow-up; w = week;
All cycles are 28-day cycles: the first visit of a cycle should be 4 weeks after the start of the previous cycle.

Because there is no infusion on these days, there is no requirement for the timing of the sample collection.

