IgA, IgM, IgG (M-component serum)	X	X			X		X				X		X	X	X	
M-component (24-hour urine sample) ^o	X	X			X		X				X		X	X	X	
Free light chain kappa, lambda, and ratio (serum)	X	X			X		X				X		X	X	X	
New cancer assessment ^p																X

Key: CT = computed tomography; d = day; ECG = electrocardiogram; ECOG = Eastern Cooperative Oncology Group; EOT = End of Trial; FU = Follow-up; Ig = immunoglobulin; w = week

- All cycles are 28-day cycles; the first visit of a cycle should be 4 weeks after the start of the previous cycle.
- Informed consent may be obtained outside of the Screening Visit window, ie, before the Screening Visit date.
- Signs and symptoms (nonserious adverse events) occurring between the Screening Visit (before the first infusion) and the first study drug treatment at Cycle 1 Visit 1 should be recorded as medical history.
- d Vital signs, defined as blood pressure, pulse, and temperature will be measured at the following time points on days when daratumumab infusions are given: just before the planned infusion start time; at 15-minute intervals during the first 2 hours of the infusion; at 60-minute intervals after the first 2 hours during the infusion; at the end of the infusion; and after the infusion at 10 minutes, 30 minutes, 1 hour, and 2 hours.
- Electrocardiograms (ECGs) will be performed at the Screening Visit (before the first infusion), before and after each daratumumab infusion, and at the EOT Visit. Three baseline ECGs should be performed before the first infusion of study drug. Before the ECGs are recorded, the subjects must be resting in a horizontal position for at least 20 minutes
- The computed tomography scan and bone marrow biopsy/aspirate may have been performed within 6 weeks before Cycle 1 Visit 1.
- To be completed as indicated to confirm response at the subsequent bone marrow biopsy visit or to investigate new symptoms, and at physician discretion.
- h Unless otherwise stated, all blood and urine samples must be taken before administration of daratumumab.
- Blood samples drawn for biochemistry assessments will be analyzed for the following: sodium, potassium, blood urea nitrogen, creatine, aspartate aminotransferase, alanine aminotransferase, alkaline phosphatase, bone-specific alkaline phosphatase, albumin, calcium, glucose, total creatinine kinase, total bilirubin, lactic dehydrogenase, uric acid, β₂-microglobulin, and C-reactive protein.

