- Blood samples drawn for hematology assessments will be analyzed for the following: red blood cell count, hemoglobin, hematocrit, mean corpuscular volume, mean corpuscular hemoglobin, mean corpuscular hemoglobin concentration, white blood cell count with differential, platelet count, and reticulocyte count.

Table 1: Phase 1 Time and Events Schedule

Note: As of Amendment 8, all subjects are to follow the Time and Events Schedule in Table 4 (see Attachment 9 for additional details)

- Blood samples for serum pregnancy tests will be collected at the Screening Visit (before the first infusion), every 4 weeks during the treatment and follow-up periods, and at the EOT Visit.
- Blood samples for analysis of complement (CH50) must be drawn 2 hours after the end of infusions.
- m Blood samples will be collected for pharmacokinetic assessments at the following time points: before infusion and at the end of infusion on all daratumumab infusion days; at 2, 5, and 12 hours after the end of infusion at Cycle 1 Visit 2 (first full-dose daratumumab infusion); at 2 hours after the end of infusion at Cycle 2 Visit 4; at each Follow-up Visit; and at the EOT Visit.
- Direct and indirect Coombs tests will be performed at all daratumumab infusion visits (before infusion and 2 hours after the end of infusion) and all follow-up visits until no antibodies are detected. These tests will also be performed at the EOT Visit for all subjects, including those who withdraw from the study.
- o In addition to quantitation of M-component, urinalysis for total protein (including albumin) and creatinine clearance will be performed.
- ^p Subjects will be contacted and asked about the occurrence of new cancers every 6 months for 3 years after their last dose of lenalidomide.

Table 2: Phase 2 Time and Events Schedule

Note: As of Amendment 8, all subjects are to follow the Time and Events Schedule in Table 4 (see Attachment 9 for additional details)

		Study Visits														
Assessments	Screening	Cycle 1						Сус	le 2ª		Cycle 3	8-6 ^a	Cycle 7+	FU ^r	ЕОТ	Safety FU
Visit Number	0	1	2	3	4	5	1	2	3	4	1	2	1		_	
De West Messale	≤21 days before Cycle 1	0d Phase 1	1.1			2	1.1			2	1.1		1.1	0.0		
Day/Week/Month Visit Window	Visit 1	only	1d	1w ±1d	2w	3w ±1d	1d	1w	2w	3w ±1d	1d ±4d	2w ±1d	1d ±4d	Q8w ±7d	±2d	
			_	±10	±10	±10	±4d	±10	±10	±10	±4a	±10	± 40	±/a	±2a	±/a
Clinical Assessments Informed consent	X ^b														-	
Eligibility criteria	X														-	
Demographics	X															

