3. STUDY DESIGN AND RATIONALE

3.1. Overview of Study Design

This is an open-label, multicenter Phase 1/2 safety study of daratumumab in combination with Len/Dex in the treatment of subjects with relapsed or relapsed and refractory multiple myeloma. The dose escalation portion of the study (Phase 1) will be a standard 3 + 3 design and will evaluate daratumumab, at doses from 2 mg/kg up to a maximum of 16 mg/kg, in combination with Len/Dex in 28-day treatment cycles. The standard "3 + 3" rules for dose escalation will be applied, However, if the study sites have identified 4 eligible subjects to start a new dose level, all 4 subjects may be enrolled. The MTD will be defined as the highest dose of the combination regimen at which less than 33% of subject's experience DLT. A recommended Phase 2 dose (RP2D) will be determined during Phase 1. The MTD or any dose evaluated in the range of 2 to 16 mg/kg of daratumumab may be considered as the RP2D based on available safety,

50

PK/pharmacodynamic, and efficacy data from Phase 1. The RP2D could be selected before escalation to or completion of the 16 mg/kg cohort. Once the RP2D is determined, the expansion (Phase 2) will open to further explore the safety and efficacy of the RP2D in approximately 30 subjects.

For Phase 1 and Phase 2 of the study there will be a Screening Period followed by the first 2 treatment cycles and will consist of weekly daratumumab infusions, totaling 4 infusions during each 28-day cycle. Cycles 3 through 6 will consist of daratumumab infusions administered every other week; Cycle 7 and all subsequent cycles will consist of monthly daratumumab infusions. The combination treatment may continue until the subject experiences disease progression or unacceptable toxicity, whichever comes first. For Phase 1 only, to minimize the risk of cytokine release syndrome, the first infusion of the first cycle will be preceded by a predose infusion the day before the scheduled full-dose infusion. The predose infusion will be 10% of the full dose, but will never be more than 10 mg in total dose. Further measures to prevent cytokine release syndrome will include premedication with antihistamines, acetaminophen, and dexamethasone before each daratumumab infusion (both predose and full dose).

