6.1. Daratumumab

Daratumumab will be administered as an IV infusion. Each subject's dose will be calculated based on the subject's weight rounded to the nearest kilogram, ie, assigned cohort dose in $mg/kg \times body$ weight in kg. The dose does not need to be recalculated for weight changes that are <10% from baseline. The weight will be used to determine the number of vials required for dosing. The pharmacist will then calculate the required volume of daratumumab from the number of vials needed for each subject. For subjects whose body mass index is greater than 30 kg/m^2 , the investigator should use a weight that, based on the subject's height, corresponds to a maximum body mass index of 30.

For Phase 1, daratumumab will be given as follows:

- Cycle 1: Day 0 (predose infusion), Day 1 (first full-dose infusion), and Days 8, 15, and 22 of a 28-day cycle
- Cycle 2: Days 1, 8, 15, and 22 of a 28-day cycle
- Cycles 3-6: Days 1 and 15 of a 28-day cycle for 4 cycles or until the subject experiences unacceptable toxicity or disease progression, whichever comes first
- Cycles 7+: Day 1 of a 28-day cycle until the subject experiences unacceptable toxicity or disease progression, whichever comes first

For Phase 2, daratumumab will be given as follows:

- Cycle 1: Day 1 (first full-dose infusion), and Days 8, 15, and 22 of a 28-day cycle
- Cycle 2: Days 1, 8, 15, and 22 of a 28-day cycle
- Cycles 3-6: Days 1 and 15 of a 28-day cycle for 4 cycles or until the subject experiences unacceptable toxicity or disease progression, whichever comes first
- Cycles 7+: Day 1 of a 28-day cycle until the subject experiences unacceptable toxicity or disease progression, whichever comes first Table 5 and Table 6 provide recommendations for the rate of infusion.

Table 5: Phase 1 Infusion Rate Recommendations

Predose	Infusions	First Full-do	ose Infusion ^a	Subsequent Full-dose Infusions ^a			
Time (minutes)	Rate (mL/hour)	Time	Rate (mL/hour)	Time (minutes)	Rate (mL/hour)		
		(minutes)					
0 - 240	12.5	0 - 60	50	0 - 60	50°		
		61 – 180	100	61 - 120	100		
		181 -	150 ^b	121 - 180	150		
				181 -	200		
Total volume	50 mL	Total volume	1000 mL	Total volume	1000 mL		

^a Additional details for administration times and rates for the full-dose infusions will be provided in the administration guidelines.

Table 6: Phase 2 Infusion Rate Recommendations

	e Infusion for y 20 Subjects ^a		e Infusion for y 10 Subjects ^a	Subsequent Full-dose Infusion for all subjects ^a			

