7. PHARMACOKINETICS/PHARMACODYNAMICS/IMMUNOGENICITY

7.1. Pharmacokinetics

PK analyses will be performed on the pharmacokinetic-evaluable population, defined as all treated subjects whose PK profiles allow accurate calculation of at least one of the PK parameters.

For Phase 1, descriptive statistics will be used to summarize daratumumab serum concentrations at each sampling time point and for each PK pharmacokinetic parameter. Concentrations below the lower quantifiable concentration will be treated as zero in the summary statistics. Mean (SD) serum daratumumab concentrations-time profiles will be plotted for the first full-dose administration and separately for peak and trough serum concentrations throughout treatment.

For Phase 2, Descriptive statistics will be used to summarize daratumumab serum concentrations at each sampling time point. Concentrations below the lower quantifiable concentration will be treated as zero in the summary statistics.

If sufficient data are available, population pharmacokinetic analysis of serum concentration-time data of daratumumab will be performed using nonlinear mixed-effects modeling. If the population pharmacokinetic analysis is conducted, details will be provided in a population pharmacokinetic analysis plan, and results of the analysis will be presented in a separate report.

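### Table 10 exempts Phase 1 pre-infusion PK samples in Cycles 7-24 from any timing rule by wrongly stating that these are not infusion days, and the SAP has no check to keep a late draw out of the trough summaries

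*Protocol*

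**What the plan says.** Table 10 (Protocol 9.2.4) lists when Phase 1 serum samples for daratumumab are drawn. In its *Before infusion* row the last three entries, for Cycle 7-24, Follow-up and EOT, carry marker b. Footnote a concerns cycle length. The other footnote, which is therefore b, reads "Because there is no infusion on these days, there is no requirement for the timing of the sample collection".

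The rest of the protocol describes Cycle 7 onward differently:

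- Section 6.1, Phase 1 dosing: "Cycles 7+: Day 1 of a 28-day cycle until the subject experiences unacceptable toxicity or disease progression, whichever comes first".
- Section 3.1: "Cycle 7 and all subsequent cycles will consist of monthly daratumumab infusions".
- Table 10 has a row headed "End of infusion", and that row is marked in the Cycle 7-24 column.
- Table 1 footnote m requires Phase 1 PK samples "before infusion and at the end of infusion on all daratumumab infusion days", and lists Follow-up and EOT samples separately.
- Table 1 footnote h gives the general default: "Unless otherwise stated, all blood and urine samples must be taken before administration of daratumumab".

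For analysis, SAP 7.1 plots Phase 1 mean (SD) concentrations "separately for peak and trough serum concentrations throughout treatment". SAP 2.1 presents data over time by the cycle, day and time point entered in the eCRF, unless specified otherwise. Protocol 9.2.6 and 11.5 name Cmin as a PK parameter.

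**The concern.** The footnote gives a false reason for waiving a timing rule, and it does so at visits where timing decides what the sample measures. A draw just before an infusion is a trough. A draw after the infusion has started is not, and one taken near its end is close to a peak.

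Footnote h does not resolve the conflict, because it yields wherever something else is stated, and footnote b states something else. Footnote m contradicts footnote b directly, so a Phase 1 site had two PK tables giving different instructions for the same visit.

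The SAP would not catch the result. A late sample entered under the pre-infusion time point stays there, because the by-week windows in SAP 2.1 work on study day and cannot separate draws before and after an infusion on one day. No rule in SAP 7.1 compares draw time with infusion start. The error runs one way: it makes troughs during maintenance dosing look higher than they are. These samples include every on-treatment Phase 1 trough at the 4-weekly interval.

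**Working it through.** **Where the marker falls.** After Screening, Table 10 has 5 (Cycle 1) + 4 (Cycle 2) + 2 (Cycles 3-6) + 1 (Cycle 7-24) + Follow-up + EOT = 14 columns. The *Before infusion* row has 11 plain marks (5 + 4 + 2) and then 3 marked b, so b falls on Cycle 7-24, Follow-up and EOT. The end-of-infusion row has 12 marks (5 + 4 + 2 + 1). The twelfth is Cycle 7-24, and Follow-up and EOT are blank. Table 10 therefore contradicts its own footnote.

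**How many samples are exposed.** Planned full-dose pre-infusion samples per subject through Cycle 24, from section 6.1:

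- Cycle 1: 4; Cycle 2: 4; Cycles 3-6: 4 × 2 = 8; Cycles 7-24: 18.
- Total 34, of which the footnote releases 18/34 = 53%.

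Cycle 7 Day 1 follows Cycle 6 Day 15, so it is a 2-week trough. The other 17, from Cycle 8 on, are 4-weekly.

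The 18 is a maximum. The Amendment 6 log says Phase 1 PK timing then moved to the Phase 2 schedule, after Phase 1 subjects had been treated for more than 12 months. Twelve months is 365/28 ≈ 13 cycles. If the footnote was in force over that time, a subject still on treatment had reached about Cycle 13 and given about 7 exposed samples.

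**Illustrative size.** The plan gives no figure to reproduce. Inputs, from section 3.2.3.1 (model prediction for 8 mg/kg weekly): peak 200 to 300 µg/mL, trough about 100 µg/mL, so peak/trough ratio R = 2 to 3. If a fraction f of the values in a mean are drawn at full peak, the mean trough is multiplied by 1 + f(R − 1).

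- 3 subjects, one mistimed (f = 1/3): (100 + 100 + 200)/3 = 133 to (100 + 100 + 300)/3 = 167, that is +33% to +67%.
- 6 subjects, one mistimed (f = 1/6): (5 × 100 + 200)/6 = 117 to (5 × 100 + 300)/6 = 133, that is +17% to +33%.

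These assume a draw at full peak. An early draw does much less. At Table 5 rates a subsequent infusion delivers 50 mL in the first hour out of 1000 mL, or 5%. If concentration rises in proportion to volume infused, a draw at one hour reads 100 + 0.05 × (100 to 200) = 105 to 110. A 3-subject mean then rises by 5/300 to 10/300, about 2% to 3%.

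For a given dose, a 4-weekly trough lies below a weekly one, so the relative error of a peak-time draw would be larger. The documents do not allow that to be quantified.

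**The case against.** The strongest reply is that the table is history and its wording largely protects itself. Section 9.2.4 stops blood sampling as of Amendment 8, and Table 1 sends all subjects to Table 4, so moving the marker changes no future draw. The row is still headed *Before infusion*, the same column asks separately for an end-of-infusion sample, and footnote m has no exception clause. Footnote b is conditional, so on an infusion day its stated reason fails. Sites also had a laboratory manual, which is not among these documents. Draw times (section 9.2.4) and infusion start and stop times (section 7) are recorded, and section 11.5 says excluded samples will be documented.

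All of this stands, and it limits the point to interpretation of data already collected. It does not remove it: recording the times makes a late draw detectable, but neither document says that anyone will look.

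A reader might infer three stronger things that the documents do not support:

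- **That the Phase 1 late-cycle troughs are in fact inflated.** Nothing shows that any sample was mistimed.
- **That the percentages above estimate the bias.** They borrow a weekly 8 mg/kg prediction for 4-weekly dosing in cohorts from 2 to 16 mg/kg, and assume one full-peak draw. Extrapolating the weekly decline over four weeks would give ratios of 2⁴ = 16 to 3⁴ = 81, but the protocol describes non-linear clearance, so those are not usable.
- **That the Phase 2 dose rests on these troughs.** None of the reasons in section 3.2.3.2 cites Phase 1 troughs from Cycle 7 onward.

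**Conclusion.** The contradiction is established: footnote b is wrong for Cycle 7-24, and it conflicts with sections 3.1 and 6.1, Table 1 footnote m and Table 10's own end-of-infusion row. The consequence is a possibility, not a finding. Where a site relied on the footnote, a post-start draw could enter the Phase 1 trough plots and Cmin, and always in the upward direction.

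The scope is narrow: descriptive Phase 1 summaries from Cycle 7, on samples already taken. The primary endpoint (incidence of adverse events), ORR and the RP2D are untouched. Phase 2 PK has its own explicit rule (Table 2 footnote l), which bars a pre-infusion draw after the infusion has started. Because the mistiming rate is unknown, the size can only be illustrated. For one late sample in a 3-subject mean it runs from about 2% (one hour into the infusion) to 67% (full peak), under the weekly 8 mg/kg assumption.

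**What to change.** - **Protocol Table 10:** limit marker b to Follow-up and EOT, so that the table agrees with Table 1 footnote m. As sampling has ended, this corrects the record only.
- **SAP 7.1:** label a Phase 1 value as a trough only if its recorded draw time precedes the recorded infusion start on that day. Exclude later draws from the trough and Cmin summaries, and list them. This is the part that still has an effect.

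The cost is one footnote marker and one SAP sentence, plus a comparison of two times already collected. The downside is that a few samples may leave the trough summary, which matters somewhat in cohorts of 3 to 6. The listing keeps them visible.
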